Participants who met eligibility criteria on the screening survey were presented with an information statement for the full longitudinal study. Upon providing electronic consent, participants completed a 30-35 minute baseline assessment. At the completion of the baseline survey, students were asked to schedule a training session conducted either in-person or virtually via Zoom. Prior to the training session, participants were randomized to one of two conditions (i.e., intervention condition or assessment-only control condition) by computer algorithm and stratified on biological sex, typical drinks per week, and college status. During the training session, participants were shown a PowerPoint presentation to aid in a discussion of the EMA survey process and study procedures, had the opportunity to ask study staff questions, and installed the web-based application on their mobile phone. Participants randomized to intervention condition had the capabilities within the app for EMA data collection and for viewing intervention content, whereas those randomized to the control condition only had the ability to utilize the app for EMA data collection. After completing the training session, participants were considered enrolled in the study.

The day after the training session, participants in both conditions completed twice daily surveys in the mobile app for 21 days. Morning assessments could be completed between 8am and 1pm. Afternoon assessments could be completed between 3pm and 7pm. Participants in the intervention condition also received intervention messages twice a day (timed to occur after completion of the assessment or generated at 1pm and 7pm, whichever was sooner).

Participants were asked to completed online follow-up assessments at 1-, 6-, and 12-months post-intervention. Follow-up assessments include both an online survey and 14 days of twice-daily EMA assessments. Participants received follow-up calls, emails, and text messages at each follow-up assessment.

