## Statistical Analysis Plan

The primary aim of this paper is to examine the efficacy of the intervention on short-term (1-month versus baseline) and long-term (6- and 12-months versus baseline) alcohol outcomes using planned contrasts. Given the repeated measures design and that all outcome variables will be non-normally distributed, generalized linear mixed models (GLMMs) will be used to test intervention effects and logistic, Poisson, negative binomial, and/or gamma error distributions may be used (Hox et al., 2017; Raudenbush & Bryk, 2002). Models will be estimated using the *glmmTMB* (Brooks et al., 2017) package in R 4.2.1 (R Core Team, 2022) using maximum likelihood estimation based on the Laplace Approximation. Four models will test for intervention effects on primary alcohol outcomes. The primary outcomes will be (1) number of typical drinks per week in the past month, (2) number of HED days in the past two weeks, (3) peak eBAC in the past month, and (4) total number of negative alcohol consequences experienced in the past month. Models use data from assessments at four timepoints (screening/baseline, 1-, 6-, and 12-month follow-ups), yielding up to 1,632 Level 1 observations across 408 Level 2 cases. All models will control for sex and college type (enrollment at 2-year versus 4-year college) at Level 2. This model serves as the basis for testing intervention effects on primary alcohol outcomes: Level 1:

$$\begin{aligned} \text{Level 1: } \text{Outcome}_{ti} &= \pi_{0i} + \pi_{1i}(1\text{-month})_{ti} + \pi_{2i}(6\text{-month})_{ti} + \pi_{3i}(12\text{-month})_{ti} \\ \text{Level 2: } \pi_{0i} &= \beta_{00} + \beta_{01}(\text{Intervention})_i + \beta_{02}(\text{Sex})_i + \beta_{03}(\text{College})_i + r_{00i} \\ \pi_{1i} &= \beta_{10} + \beta_{11}(\text{Intervention})_i + r_{10i} \\ \pi_{2i} &= \beta_{20} + \beta_{21}(\text{Intervention})_i + r_{20i} \\ \pi_{3i} &= \beta_{30} + \beta_{31}(\text{Intervention})_i + r_{30i} \end{aligned}$$

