where  $t$  indexes study wave and  $i$  indexes individual participants.  $\text{Outcome}_{ti}$  represents the value of the outcome variable for a given individual at a given study wave. To test for intervention effects, time will be coded with a set of binary indicator variables (1-month, 6-month, 12-month) that compare each follow-up wave to screening/baseline (reference category). Intervention is a binary variable comparing the intervention condition to the assessment-only control condition. Of particular interest are parameters that reflect the interaction between intervention group and study wave (e.g.,  $\beta_{11}$  at 1-month). The outcome will be connected to predictor variables through a link function, which will vary based on the type of error distribution used (e.g., log link function for Poisson error distribution). Sensitivity analyses will include linear or non-linear growth models testing average monthly changes in alcohol outcomes between the control and intervention conditions rather than the planned contrasts described above.

A secondary aim will test whether the intervention resulted in long-term (12 month) reductions in level of hazardous/harmful drinking, as indicated by AUDIT scores, as compared to the control condition. This will be tested using a negative binomial regression in which AUDIT scores at the 12-month follow-up will be regressed on condition, sex, college type, and baseline AUDIT scores.

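### Efficiency, not error: the primary model gives each arm its own baseline mean although baseline precedes randomisation; a common mean is at least as precise if the covariance is correctly specified

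*SAP*

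**What the plan says.** The SAP (Statistical Analysis Plan, Level 2 equations) writes the intercept as "\beta_{00} + \beta_{01}(\text{Intervention})_i" plus sex, college type and a random effect. The time indicators "compare each follow-up wave to screening/baseline (reference category"), so β01 is the arm difference at baseline on the link scale. On the effects tested, the SAP says: "Of particular interest are parameters that reflect the interaction between intervention group and study wave". These are β11, β21 and β31. The error model is left open: "logistic, Poisson, negative binomial, and/or gamma error distributions may be used". On covariates it says: "All models will control for sex and college type".

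The Protocol gives the order of events. First: "Participants who met eligibility criteria on the screening survey were presented with an information statement for the full longitudinal study". Then: "Upon providing electronic consent, participants completed a 30-35 minute baseline assessment". Randomisation follows, before the training session, and is stratified on sex, typical drinks per week and college status. A participant counts as enrolled only once training is complete.

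For the secondary AUDIT outcome the SAP takes a different route: the baseline score is a covariate.

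**The concern.** Among all randomised participants the two arms share one baseline distribution, so β01 is zero by design. Estimating it discards that knowledge. Each effect then subtracts the whole chance baseline difference from the follow-up difference. A common-baseline model subtracts only the part that the baseline-to-follow-up correlation justifies, much as the AUDIT analysis does.

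At stake is power for the three follow-up contrasts on each of four primary outcomes, using data already being collected. Stratifying on drinks per week changes the nature of the gain. Where stratification has already balanced baseline, the planned estimate is not very noisy, but its model-based standard error does not reflect that balance, because the model adjusts only for sex and college type. The test is then conservative.

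**Working it through.** **Plan's own figure.** The SAP gives "yielding up to 1,632 Level 1 observations across 408 Level 2 cases". 408 × 4 = 1,632, which confirms that baseline is one of four outcome waves.

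**Assumed inputs (none is in the documents).** 1:1 allocation; two-sided 5% test; correlation ρ between baseline and follow-up; k = baseline SD / follow-up SD; stratification bands.

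**Linear analogue, complete data, known covariance, no stratification.** In units of follow-up variance × (1/n1 + 1/n2):

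- planned contrast: 1 + k² − 2ρk = (1 − ρ²) + (k − ρ)²
- common-baseline contrast: 1 − ρ²

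The difference, (k − ρ)², cannot be negative and is zero when k = ρ. The SE ratio, common over planned, is √[(1 − ρ²)/(1 + k² − 2ρk)]:

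| k | ρ = 0.4 | 0.5 | 0.6 | 0.7 |
|---|---|---|---|---|
| 0.7 | 0.950 | 0.974 | 0.992 | 1.000 |
| 0.8 | 0.917 | 0.945 | 0.970 | 0.990 |
| 1.0 | 0.837 | 0.866 | 0.894 | 0.922 |
| 1.2 | 0.753 | 0.778 | 0.800 | 0.819 |

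The saving is therefore 0% to 25%. For a contrast with 80% power as planned, the new power is Φ(2.80/ratio − 1.96). At ρ = 0.6 and k = 1 this is Φ(2.80/0.894 − 1.96) = 88%. At k = 0.7, 0.8 and 1.2 it is 81%, 82% and 94%.

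**With dropout.** At equal SDs and assumed retention of 90/85/80%, the variance ratio was 0.77 to 0.79 at ρ = 0.5 (0.75 without dropout) and 0.86 to 0.87 at ρ = 0.7 (0.85 without).

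**With stratification on drinks per week.** Let c be the outcome's baseline correlation with drinks, and R² the share of drinks variance explained by the bands (0.637 for two equal bands, 0.861 for four). Follow-up is assumed to relate to drinks only through baseline. With f = 1 − c²R²:

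- common-baseline variance: 1 − ρ²
- planned, true: 1 − ρ² + (k − ρ)²f
- planned, as the model reports it: 1 − ρ² + (k − ρ)²

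For drinks per week (c = 1), four bands, k = 1, ρ = 0.6: f = 0.139. The three variances are 0.640, 0.640 + 0.160 × 0.139 = 0.662, and 0.800. The true SE saving is 1 − √(0.640/0.662) = 1.7%. The planned test rejects under no effect with probability 2Φ(−1.96 × √(0.800/0.662)) = 3.1%.

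At k = 1, over ρ 0.4 to 0.7 and two or four bands:

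| Outcome | True SE saving | Rejection at nominal 5% |
|---|---|---|
| Drinks per week (c = 1) | 1–7% | 2.3–3.9% |
| Outcome with c = 0.6 | 6–13% | 4.0–4.6% |

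Power from 80%, with four bands, ρ = 0.6 and k = 0.7/0.8/1.0/1.2, becomes 80.4/81.7/86.2/91.4% for drinks per week and 80.5/82.1/87.3/93.1% for c = 0.6. A simulation with n = 408 and 8,000 runs (k = 1, ρ = 0.6, four bands) gave 78.1% planned and 84.8% common baseline for c = 1, and 79.6% and 86.8% for c = 0.6.

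**Log-link models.** Fixing a parameter at its true value cannot raise the large-sample variance of the others in a correctly specified model. Four-wave information calculations (unstratified, no effect, complete data, wave-specific normal effects, assumed means and dispersions, latent correlation 0.5 to 0.8) gave SE savings of 8–16% for Poisson and 10–24% for negative binomial or gamma. These used adaptive quadrature. The saving in the SAP's Laplace fits is not established.

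**Where the ordering fails.** Suppose the random effects are reduced to an intercept, so the working covariance has one variance and one correlation w. The common-baseline estimate then subtracts w times the baseline difference. At k = 0.7, ρ = 0.6 the average variance is (0.49 + 3)/4 = 0.8725 and the average covariance is (3 × 0.42 + 3 × 0.60)/6 = 0.51, so w = 0.585. True variances are 1 + 0.585² × 0.49 − 2 × 0.585 × 0.42 = 0.676 (common) and 1 + 0.49 − 0.84 = 0.650 (planned). The common-baseline SE is 2.0% larger. It is 4.7% larger at k = 0.7, ρ = 0.7 and 1.1% larger at k = 0.8, ρ = 0.7.

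**Loss between randomisation and training.** In a simulation with no effect, one arm lost 20% above the median and 5% below it, the other 5% throughout (ρ 0.4 to 0.7):

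| Loss driven by | Bias, planned | Bias, common baseline |
|---|---|---|
| Observed baseline | 0.040 to 0.021 SD | about 0 |
| Unobserved stable trait | about 0 | −0.027 to −0.017 SD |

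**The case against.** The written model is a recognised specification and matches the SAP's stated aim of comparing each follow-up with baseline. A reader might infer that its contrasts are biased or its tests invalid. The documents do not support that: the contrasts are valid, and a conservative test is not a validity problem. Nor do they support a reading that the trial is underpowered, since they state no power, effect size, SD or correlation; the 80% above is only a reference point.

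A reader might also infer that the change is free and never loses precision. Neither holds without conditions. The SAP specifies four random effects per person with at most four observations each, and names no fallback if the fit fails. A reduction to a random intercept, which is an assumption here and not SAP text, can reverse the ordering. The zero baseline difference is also guaranteed only for everyone randomised, and the documents do not say whether the 408 are all randomised or only those who completed training. Under trait-driven loss the written model is the less biased one. Under baseline-driven loss it is the more biased one, so estimating β01 is not general protection either.

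Finally, the Protocol is in the past tense and the SAP gives an exact number of cases, which suggests that data collection was well advanced. That does not show that outcomes had been analysed by arm, but it limits what can still be changed. These objections limit the claim and shape the fix. They do not remove the case for using a design fact that the model ignores.

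**Conclusion.** The point stands as a recommended efficiency improvement. Given a covariance that lets variance differ by wave and is correctly specified, a common baseline mean cannot lose precision in the linear analogue with known covariance, and the same holds in large samples for the mixed model. The size cannot be fixed from the documents. It may be negligible when baseline SD is close to ρ times follow-up SD, and substantial when baseline is as variable as follow-up or more so. More of the gain is real precision for HED days, peak eBAC and consequences, to the extent that they are only partly correlated with drinks; for drinks per week it lies mostly in correcting an overstated standard error. All figures rest on the assumptions listed in the working.

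**What to change.** By a documented amendment made before any unblinded outcome analysis:

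- Remove β01(Intervention) from the intercept equation. In code, enter the three wave indicators and their three products with condition, with no condition main effect.
- Keep baseline in the outcome vector, β11, β21 and β31 as the 1-, 6- and 12-month effects, and sex and college type as covariates.
- Keep the wave-specific random effects, or name another covariance that lets variance differ by wave. Do not fall back to a random intercept alone with this parameterisation.
- Keep the written model, with β01 estimated, as a sensitivity analysis.
- State whether the 408 are all randomised or only trained participants, and report loss between randomisation and training by arm.

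If outcomes have already been analysed by arm, leave the primary model as written and report the common-baseline model only as a labelled post hoc sensitivity analysis.

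The cost is one term, one amendment and one extra model run per outcome, with no new data. The price in assumptions is reliance on a shared baseline mean in the analysed set, which is why the loss by arm and both models should be shown.

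### The 12-month AUDIT regression leaves out typical drinks per week, the third stratification factor; the likely cost is about 1% in standard error, and possibly none.

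*SAP*

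**What the plan says.** The protocol's account of randomization has participants allocated by computer algorithm, "stratified on biological sex, typical drinks per week, and college status". It gives no cut-points for drinks per week, block sizes or allocation ratio.

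The last paragraph of the Statistical Analysis Plan sets the secondary aim: long-term "reductions in level of hazardous/harmful drinking, as indicated by AUDIT scores". The chosen method is a negative binomial model, and the SAP lists its terms in one clause: "AUDIT scores at the 12-month follow-up will be regressed on condition, sex, college type, and baseline AUDIT scores". Typical drinks per week is not among the covariates.

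The variable is available. The first primary outcome is "number of typical drinks per week in the past month", and screening/baseline is one of the four timepoints in the primary models. For those models the SAP says "All models will control for sex and college type (enrollment at 2-year versus 4-year college) at Level 2".

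**The concern.** A stratification factor is normally chosen because it is expected to predict outcome. Here the plan adjusts the AUDIT analysis for sex and college type and omits the one stratification factor that directly measures drinking. The outcome is itself a measure of hazardous drinking, so baseline consumption is a natural prognostic covariate. The available text gives no reason for leaving it out. Part of the SAP was not in that text, so I do not claim that no reason exists.

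What is at stake is efficiency. If baseline drinks predict 12-month AUDIT beyond baseline AUDIT, sex and college type, leaving them out makes the standard error of the condition effect larger than it need be.

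**Working it through.** **Figure in the plan.** The SAP gives no standard error, power or sample-size figure for the AUDIT analysis. Its one checkable count is "yielding up to 1,632 Level 1 observations across 408 Level 2 cases": 408 × 4 = 1,632, which reproduces. The AUDIT model uses one record per participant, so at most 408.

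**Inputs.** Let D be baseline drinks per week, A baseline AUDIT and Y 12-month AUDIT. The documents give none of their correlations, so all three are assumed:
- r(D,A) from 0.4 to 0.5
- r(A,Y) from 0.5 to 0.6
- r(D,Y) from the product r(D,A) × r(A,Y), where drinks add nothing to baseline AUDIT, up to 0.45

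**Formulas** (linear-model approximation):
- Partial R² of D given A = (r_DY − r_DA·r_AY)² / [(1 − r_DA²)(1 − r_AY²)]
- SE without D / SE with D = 1/√(1 − R²)
- Equivalent participants lost = 408 × R²
- Power without D, if the model with D has 80% at two-sided 5% (illustrative; the available text gives no power) = Φ(2.80·√(1 − R²) − 1.96)

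**Midpoint of the assumed ranges.** With r_DA = 0.45 and r_AY = 0.55 the product is 0.2475. The midpoint for r_DY is (0.2475 + 0.45)/2 = 0.349.
- R² = (0.349 − 0.2475)² / (0.7975 × 0.6975) = 0.01025/0.5563 = 0.018
- SE ratio = 1/√0.982 = 1.009
- Participants = 408 × 0.0184 = 7.5, about 8
- Power about 79%

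**Across the range** (the last row lies outside it):

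| r_DA, r_AY, r_DY | Partial R² | SE ratio | Participants of 408 | Power |
|---|---|---|---|---|
| 0.5, 0.6, 0.30 (no added information) | 0 | 1.000 | 0 | 80% |
| 0.45, 0.55, 0.349 (midpoint) | 0.018 | 1.009 | 8 | 79% |
| 0.45, 0.55, 0.40 | 0.042 | 1.022 | 17 | 78% |
| 0.4, 0.5, 0.45 (largest in range) | 0.099 | 1.054 | 40 | 76% |
| 0.4, 0.5, 0.50 | 0.143 | 1.080 | 58 | 74% |

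A uniform sweep of the assumed ranges gives a median SE cost of 0.9% and a mean of 1.3%.

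**Does the approximation carry over to negative binomial regression?** It was checked by simulation with n = 408, assumed AUDIT mean 9 and shape 2.5, allocation balanced within sex × college × median drinks, no effect, and 10,000 runs per setting.
- At (0.5, 0.6, 0.30), (0.4, 0.5, 0.30), (0.45, 0.55, 0.40) and (0.4, 0.5, 0.45) the SE ratios were 1.001, 1.008, 1.021 and 1.051. The formula gives 1.000, 1.008, 1.022 and 1.054.
- Type I error was 0.046 to 0.056 without drinks and 0.052 to 0.056 with them.
- A repeat with unstratified 1:1 allocation and n = 326 (80% retention assumed) gave ratios of 1.000 to 1.048, so the SE result does not hinge on the unstated stratification details.

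These simulations start from the same assumed correlations. They support the formula, not the inputs.

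**The case against.** The strongest reply is that no error has been shown. The SAP does not promise to adjust for every stratification factor. The AUDIT model follows the pattern of the primary models: sex, college type and the outcome's own baseline, which in the primary models enters as a repeated measure. Baseline AUDIT is the most direct baseline measure of the outcome and may leave drinks per week with nothing to add. This stands, and it is why the range starts at zero and the point is minor. It does not show a drawback to adding the variable.

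It can also be said that every magnitude is assumed. That stands too. A partial correlation of 0.305 gives a 5% cost, and 0.40 would give 1/√(1 − 0.16) = 1.091, or 9%. The upper end therefore depends on where the assumed range is cut.

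A reader might infer more than the documents support:
- **That about 5% is the expected cost.** It is the largest value in the assumed range; the centre is near 1%.
- **That the analysis is biased or its test invalid.** Allocation is randomized, so omitting a prognostic baseline variable does not bias the condition effect, and the simulations show no meaningful inflation of type I error.
- **That the test is materially conservative.** This can happen when a stratification factor is left out, but its size depends on cut-points and blocking that the documents do not give, so none is claimed.
- **That the primary models must change.** The models for HED days, peak eBAC and consequences also omit baseline drinks, and the same question could be asked of them. But each has its own outcome's baseline among the repeated measures and tests the intervention-by-wave terms. The calculation here does not apply to them, and no cost has been shown.

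**Conclusion.** The point holds as a minor one. Typical drinks per week was used to stratify randomization, is collected at screening/baseline, and is missing from the 12-month AUDIT regression. The consequence is possible lost precision in one secondary analysis: a standard error 0 to about 5% larger under the assumed correlations, centrally about 0.9%. That is roughly 8 of 408 participants, or power of about 79% where the adjusted model would have 80%. The loss is nil if baseline AUDIT already holds the information in drinks. Confidence in the omission is high. Confidence in its size is limited, because the documents supply none of the three correlations.

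**What to change.** Add baseline typical drinks per week to the AUDIT regression in one form fixed in advance. Continuous log(1 + drinks per week) would serve, and so would the category used for stratification; the documents do not favour either. What matters is that a single form is named, so that the choice cannot follow the results. If the omission is deliberate, a sentence giving the reason would remove the inconsistency.

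The cost is small: no new data, and one degree of freedom for a continuous or two-level term out of up to 408 participants. Timing needs care, because the protocol, dated May 24, 2024, already describes recruitment and baseline procedures in the past tense. The change should be dated before 12-month AUDIT is analysed by arm. If that analysis has been done, keep the planned model as the secondary analysis and report the adjusted model as a labelled sensitivity analysis. On this point the four primary models can stay as they are.
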